8.2. Analysis Sets

8.2.1. Full Analysis Set

The full-analysis set (FAS) includes all subjects who receive at least 1 dose of study treatment ENTO. This analysis set will be used in the analyses of subject characteristics, exposure, safety, and efficacy. Summary and listing will be presented by study group, dose level, treatment arm, cohort, and overall if applicable.

For analysis by dose levels, subjects from phase 1b and phase 2 will be pooled and analyzed by the dose level first received, unless otherwise specified.

8.2.2. DLT Analysis Set

DLT analysis set includes subjects in FAS with sufficient drug exposure or experience a DLT during the DLT assessment window (see Section 3.2).

8.2.3. Pharmacokinetic Analysis Sets

The pharmacokinetic analysis sets include data from subjects in the full analysis set who have the necessary baseline and on-study measurements to provide interpretable results for the specific parameters of interest.

These analysis sets will be used in the analyses of ENTO plasma pharmacokinetics.

8.3. Data Handling Conventions

8.3.1. General Methods

By-subject listings will be created for important variables from each eCRF module. Summary tables for continuous variables will contain the following statistics: N (number in population), n (number with data), mean, standard deviation, 95% confidence intervals (CIs) on the mean, median, minimum, and maximum. Summary tables for categorical variables will include: N, n, percentage, and 95% CIs on the percentage. Unless otherwise indicated, 95% CIs for binary variables will be calculated using the binomial distribution (exact method) and will be 2 sided. Data will be described and summarized by dose level, analysis set, and timepoint. As appropriate, changes from baseline to each subsequent timepoint will be described and summarized. Similarly, as appropriate, the best change from baseline during the study will also be described and summarized. Graphical techniques (eg, waterfall plots, Kaplan-Meier curves, line plots) may be used when such methods are appropriate and informative.

The baseline value used in each analysis will be the last (most recent) pre-treatment value. Data from all sites will be pooled for all analyses. Analyses will be based upon the observed data unless methods for handling missing data are specified. If there is a significant degree of non-normality, analyses may be performed on log-transformed data or nonparametric tests may be applied, as appropriate.

Unless otherwise specified, all analyses will be 2-sided at the 0.05 level of significance.

8.4. Demographic Data and Baseline Characteristics

A listing of all full-analysis subjects will be generated to describe site, subject number, first screening date, first treatment date, stage (escalation and expansion), dose level, duration of study treatment, and the reason for discontinuing study treatment. Available information on subjects who were screened or registered but not treated may be listed separately. A table will be created summarizing these categories in terms of number and percent for the full analysis set.

Subject baseline characteristics will be listed and summarized by stage and dose level for the full analysis set.

8.5. Efficacy Analysis

The efficacy of ENTO when used as monotherapy or in combination with chemotherapy will be evaluated using the International Working Group criteria {Cheson 2003}, which is documented in [Appendix 5](#).

8.5.1. Categorical Endpoints

Categorical endpoints, such as complete remission rate, composite complete remission (CR/CRi) rate, and overall response (CR/CRi/PR) rate at initial induction, will be summarized. For all analyses, the corresponding 95% exact CIs will be presented.

8.5.2. Time-to-Event Endpoints

For a subject who is not known to have relapsed or died by the end of the study follow-up or data cutoff, RFS is censored on the date of the last available assessment of the subject.

For subjects with none of the events defined in EFS before the end of the study follow-up or data cutoff, EFS is censored at the date of the last available assessment of the subject.

For a subject who is not known to have died by the end of study follow-up or data cutoff, OS is censored on the date the subject was last known to be alive.

RFS, EFS and OS will be analyzed using Kaplan-Meier (KM) methods. The KM estimate of the survival function will be computed and the results will be presented using KM curves. The median will be provided along with the corresponding 95% CI. Additionally, the 25% and 75% percentiles for these endpoints will also be provided.

For subjects who die without report of relapse, remission duration is censored on the date of death, regardless of cause. For a subject with no report of relapse by the end of the study follow-up or data cutoff date, observation is censored on the date of the last available assessment of the subject.

Analysis of remission duration will be analyzed using cumulative incidence by considering competing risks. The estimate of the cumulative incidence of relapse (CIR) will be reported with the associated 95% CI.

8.5.3. Continuous Endpoints

Continuous endpoints (eg, TTR and TTC) will be summarized using descriptive statistics.

8.6. Safety Analysis

All safety data collected on or after the date that ENTO was first dispensed up to 30 days after the date of last dose of ENTO will be summarized by dose level. For Group A and Group B, safety data will be presented by the lead-in ENTO therapy phase and the induction chemotherapy phase separately, and overall.

8.6.1. Extent of Exposure

Descriptive information will be provided by dose level regarding the number of doses of study therapy prescribed, the total number of doses taken, the percent of expected doses taken, duration of treatment, and the number and timing of prescribed dose reductions and interruptions.

ENTO compliance will be described in terms of the proportion of study treatment actually taken based on returned pill count relative to the amount that was dispensed (taking into account physician-prescribed reductions and interruptions).

8.6.2. Adverse Events

All adverse events will be listed. The focus of adverse event summarization will be on treatment emergent adverse events. A treatment-emergent adverse event is defined as an adverse event that onset in the period from the first dose of study treatment to 30 days after the permanent discontinuation of study treatment or that leads to permanent discontinuation of study treatment. Adverse events that occur before the first dose of study treatment or >30 days after the subject has been discontinued from study treatment will be included in data listings.

Adverse events will be classified using MedDRA (<http://www.meddrasso.com>) with descriptions by System Organ Class, High-Level Group Term, High Level Term, Preferred Term, and Lower-Level Term. The severity of adverse events will be graded by the investigator according to the CTCAE, Version 4.03 (http://evs.nci.nih.gov/ftp1/CTCAE/CTCAE_4.03_2010_06-14_QuickReference_8.5x11.pdf), whenever possible. If a CTCAE criterion does not exist for a specific type of adverse event, the grade corresponding to the appropriate adjective will be used by the investigator to describe the maximum intensity of the adverse event: Grade 1 (mild), Grade 2 (moderate), Grade 3 (severe), Grade 4 (life threatening), or Grade 5 (fatal). The relationship of the adverse event to the study treatment will be categorized as related or unrelated.

Treatment-emergent adverse events will be summarized. Summary tables will be presented to show the number of subjects reporting treatment-emergent adverse events by severity grade and corresponding percentages. A subject who reports multiple treatment-emergent adverse events within the same Preferred Term (or System Organ Class) is counted only once for that Preferred Term (or System Organ Class) using the worst severity grade. Adverse event descriptions will be presented in alphabetical order of System Organ Class, then by decreasing frequency in the “overall” column for a given Preferred Term.

Separate listings and summaries will be prepared for the following types of treatment emergent adverse events:

- Study-drug-related adverse events
- Adverse events that are Grade ≥ 3 in severity
- Adverse events leading to study treatment interruption and/or dose modification

- Adverse events leading to study treatment discontinuation
- Serious adverse events (with categorization of the primary reason that the adverse event is considered serious, eg, death, hospitalization, etc.)
- DLT will be listed and summarized and the DLT rate will be presented by study group and dose cohort and the corresponding 90% CIs will be presented

8.6.3. Laboratory Evaluations

All laboratory data will be listed. Summaries of laboratory data will be based on observed data and will be reported using conventional units. The focus of laboratory data summarization will be on treatment-emergent laboratory abnormalities. A treatment emergent laboratory abnormality is defined as an abnormality that, compared to baseline, worsens by ≥ 1 grade in the period from the first dose of study treatment to 30 days after the last dose of study treatment. If baseline data are missing, then any graded abnormality (ie, an abnormality that is Grade ≥ 1 in severity) will be considered treatment emergent. Laboratory abnormalities that occur before the first dose of study treatment or > 30 days after the subject has been discontinued from study treatment will be included in data listings.

Hematological, serum biochemistry, and urine data will be programmatically graded according to CTCAE severity grade, when applicable. For parameters for which a CTCAE scale does not exist, reference ranges from the central laboratory will be used to determine programmatically if a laboratory parameter is below, within, or above the normal range for the subject's age, sex, etc.

Hematological and serum biochemistry and their changes from baseline will be summarized. Summary tables will be presented for each relevant assay to show the number of subjects by CTCAE severity grade with corresponding percentages. For parameters for which a CTCAE scale does not exist, the frequency of subjects with values below, within, and above the normal ranges will be summarized. Subjects will be characterized only once for a given assay, based on their worst severity grade observed during a period of interest (eg, during the study or from baseline to a particular visit).

Shift tables for hematology and serum biochemistry will also be presented by showing change in CTCAE severity grade from baseline to each visit. For parameters for which a CTCAE scale does not exist, shift tables will be presented showing change in results from baseline (normal, low and high [or abnormal]) to each visit (normal, low and high [or abnormal]). Tables will be prepared to show frequencies adjusted for baseline values; for this frequency, subjects with the same or worse toxicity grade at baseline are not considered.

Separate listings and summaries will be prepared for laboratory abnormalities that are Grade ≥ 3 in severity.

8.7. Pharmacokinetic Analysis

Concentrations of ENTO in plasma will be determined using a validated bioanalytical assay. Plasma concentrations will be displayed as individual concentration vs. time using scheduled sampling times. Concentrations of ENTO will be listed by subject and summarized using descriptive statistics (eg, n, arithmetic mean, geometric mean, % coefficient of variation [CV], StD, median, Q1, Q3, min, and max). Mean (\pm StD) plasma concentration-time curves will be plotted in both semi-logarithmic and linear formats.

8.8.

CCI

CCI

8.9. Sample Size

In Phase 1b, each group will enroll up to 12 subjects, assuming 2 planned dose levels for escalation are tested with up to 6 subjects per level. Assuming 10% of the subjects are unevaluable during dose escalation, up to 14 subjects may be enrolled in each group for a total of up to 42 subjects. In Group B, an additional 6 subjects will be enrolled to evaluate the safety of ENTO in combination with azacitidine prior to the dose expansion.

In Phase 2, approximately 40 additional subjects will be enrolled in Group A. [Table 8-1](#) provides the 90% confidence interval (CI) of 40 subjects for the assumed composite complete remission rate. This sample size ensures a narrow CI (~ 7-14% distance from the point estimates). The composite complete remission rate of standard chemotherapy (7+3) has been reported as 52% in the CALGB study of over 1000 subjects.

Table 8-1. Exact 90% CIs of Composite Complete Remission Rate for a Cohort Size of 40 in Group A

Expected Composite Complete Remission Rate of Entospletinib + 7+3	Exact 90% CI
70%	(56% – 82%)
80%	(67% – 90%)
90%	(79% – 97%)

In the Group B phase 2, approximately 40 additional subjects will be randomized in a 1:1 manner to either treatment arm ENTO + decitabine or ENTO + azacitidine. Randomization will be stratified by age (≤ 75 or > 75 years) and WBC ($\leq 5,000/\mu\text{L}$ or $> 5,000/\mu\text{L}$). Assuming an composite complete remission rate of 50% for both treatment arms, the 90% CI would be 30% to 70% with a sample size of 20. The composite complete remission rate of standard chemotherapy is reported as 20% – 30%. Evaluation between the treatment arms will be based on the totality of clinical data.

Approximately 60 additional subjects will be enrolled in the Group C dose expansion.

A total of 15 initial subjects in Cohort C1A will be evaluated for futility. An additional 15 subjects will be enrolled if greater or equal to 5 (out of 15) CR/CRi are observed. This futility boundary will provide a high chance (84%) of early stopping of the trial if the composite complete remission rate is undesirable (20%) and a low chance (22%) of early stopping if the composite complete remission rate is clinically meaningful (40%). At this time, futility has been met, and thus, Cohort C1A will not move forward.

The sample size is 15 for Cohort C2. This sample size is based on practical considerations. The sample size is 30 for Cohort C3, which will provide adequate precision of efficacy estimates. [Table 8-2](#) provides the 90% confidence interval (CI) of 30 subjects for the assumed composite complete remission rate.

Table 8-2. Exact 90% CIs of Composite Complete Remission Rate for a Cohort Size of 30 in Cohort C3

Expected Composite Complete Remission Rate of Entospletinib Monotherapy in Cohort C3	Exact 90% CI
30%	(17% – 47%)
50%	(34% – 66%)
70%	(53% – 83%)

Therefore, a total of approximately 54 subjects (including 14 in Phase 1b and 40 in Phase 2) in Group A, approximately 60 subjects (including 14 in Phase 1b, 6 in the safety run-in of ENTO + azacitidine, and 40 in Phase 2) in Group B, and approximately 74 subjects (including 14 in Phase 1b and 60 in Phase 2) in Group C will be enrolled for the duration of the study.

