3.1.6. Group C Phase 2 (Dose Expansion): Entospletinib Monotherapy

Note: At the time of this amendment, Cohort C1A had completed enrollment (n=15). This amendment identifies the closure of Cohort C3 to further enrollment (n=12).

Relapsed/refractory and previously untreated subjects will be evaluated in separate cohorts during phase 2 as monotherapy. ENTO 400 mg will be administered orally every 12 hours on Days 1-28 of every 28-day cycle as long as the subject is experiencing benefit and does not meet criteria for study treatment discontinuation.

A bone marrow biopsy and aspirate sample will be collected for disease assessment and biomarker research at the end of Cycles 1 and 2 on Day 28. A bone marrow aspirate sample will also be collected for disease assessment and biomarker research on Day 28 of every 4 cycles beginning on Cycle 4 Day 28 (eg, Cycle 4 Day 28, Cycle 8 Day 28) and at suspected disease progression. Subjects who achieve CR/CRi that is stable for 2 consecutive bone marrow evaluations are not required to have further bone marrow aspirate samples collected, unless clinically indicated.

Cohort C1A: This cohort is designed to enroll 15 relapsed/refractory AML subjects. If 5 or more of the initial 15 subjects achieve CR/CRi after 1-2 cycles, an additional 15 subjects would then be enrolled. However, if less than 5 of the initial 15 subjects achieve CR/CRi after 1-2 cycles, then treatment would be considered futile. At this time, futility has been met and, thus, Cohort C1A will not move forward (ie, will not enroll any subjects).

Cohort C2: 15 relapsed/refractory AML subjects with MLL.

Cohort C3: 30 previously untreated AML subjects who are unfit (eg, very elderly, have multiple comorbidities, and a poor ECOG/performance status) for chemotherapy or hypomethylating agent, or refuse either of these 2 treatment options.

If a subject discontinues study treatment (eg, as a result of an AE), every attempt should be made to keep the subject in the study to perform the required study-related follow-up and procedures. If this is not possible or acceptable to the subject or investigator, the subject may be withdrawn from the study.

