In the Group B Phase 2, approximately 40 additional subjects will be randomized in a 1:1 manner to either treatment arm ENTO + decitabine or ENTO + azacitidine. Randomization will be stratified by age (≤ 75 years or > 75 years) and WBC ($\leq 5,000/uL$ or $> 5,000/uL$). Assuming a composite complete remission rate of 50% for both treatment arms, the 90% CI would be 30% to 70% with a sample size of 20. The composite complete remission rate of standard chemotherapy is reported as 20% to 30%. Evaluation between the treatment arms will be based on the totality of clinical data.

Approximately 63 additional subjects will be enrolled in Group C dose expansion.

A total of 15 initial subjects, including 9 subjects in Group C Phase 1b who were R/R AML and received at least 21 days of ENTO (400 mg or 800 mg) and 6 subjects in Cohort C1A, will be pooled for evaluation of futility in subjects with R/R AML. An additional 15 subjects will be enrolled if greater or equal to 5 (out of 15) CR/CRi are observed. This futility boundary will provide a high chance (84%) of early stopping of the trial if the composite complete remission rate is undesirable (20%) and a low chance (22%) of early stopping if the composite complete remission rate is clinically meaningful (40%).

The sample size is 15 for Cohort C2. This sample size is based on practical considerations. The sample size is 30 for previously untreated AML (unfit for Group A or B), including 3 subjects in Group C Phase 1b who were previously untreated AML, unfit for Group A or B, and received at least 21 days of ENTO (400 mg or 800 mg), and 27 subjects in Cohort C3, which will provide adequate precision of efficacy estimates. [Table 1-3](#) provides the 90% CI of 30 subjects for the assumed composite complete remission rate.

Table 1-3. Exact 90% CIs of Composite Complete Remission Rate for a Cohort Size of 30 in Subjects with Previously Untreated AML (Unfit for Group A or B)

Assumed Composite Complete Remission Rate of ENTO Monotherapy in Subjects with Previously Untreated AML (Unfit for Group A or B)	Exact 90% CI
30%	(17% – 47%)
50%	(34% – 66%)
70%	(53% – 83%)

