6.1.2. Analysis of the Primary Efficacy Endpoints

Complete remission rate, composite complete remission (CR/CRi) rate, and overall response (CR/CRi/PR) rate at induction completion for Groups A and B will be summarized and the corresponding 95% exact CIs based on Clopper-Pearson method will be presented.

Response at induction completion is defined as the best response across the time points that occurred after day 1 of last cycle of induction therapy, and prior to the earliest of cycle 1 day 1 of post-remission or maintenance therapy, date of SCT and date of other anticancer therapy (excluding SCT and conditioning regimen (listed in Appendix 2)). Best response is the best outcome according to the ranking below by decreasing favorable level:

- 1) Cytogenetic Complete Remission [CRc]
- 2) Morphologic Complete Remission [CR]
- 3) Morphologic Complete Remission with Incomplete Blood Count Recovery [CRi]

- 4) Partial Remission [PR]
- 5) Morphologic Leukemia-free State [MLFS]
- 6) Relapse
- 7) Other

The category “Other” includes 3 subcategories: Treatment Failure [TF], Early Treatment Assessment [ETA], and No Assessment Done. For subjects who had response assessment in the last cycle but didn’t achieve any of the first 6 categories listed above at induction completion, TF will be the response at induction completion for those who received 2 induction cycles in Group A or received ≥ 2 induction cycles in Group B, and ETA will be the response at induction completion for those who only received ≤ 1 induction cycle. All subjects in “Other” will be considered as nonresponders and will be included in the denominator when calculating the remission rates at induction completion.

Complete remission rate, composite complete remission (CR/CRi) rate, and overall response (CR/CRi/PR) rate per best overall response ever achieved during the treatment for Group C will be summarized and the corresponding 95% exact CIs based on Clopper-Pearson method will be presented.

Best overall response is defined as the best response across all time points prior to SCT and other anticancer therapy (excluding SCT and conditioning regimen). Best response is the best outcome according to the ranking below by decreasing favorable level:

- 1) Cytogenetic Complete Remission [CRc]
- 2) Morphologic Complete Remission [CR]
- 3) Morphologic Complete Remission with Incomplete Blood Count Recovery [CRi]
- 4) Partial Remission [PR]
- 5) Morphologic Leukemia-free State [MLFS]
- 6) Other

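### Does it matter that the cohort sizes are justified with 90% confidence intervals when response rates will be reported with 95% intervals?

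*Protocol*

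**What the plan says.** The sizing text works at the 90% level. Protocol 8.9 gives exact 90% intervals for composite complete remission in Group A Phase 2 (Table 8-1, n=40) and summarises them: "This sample size ensures a narrow CI (~ 7-14% distance from the point estimates". For each Group B arm, at an assumed 50% rate, "the 90% CI would be 30% to 70% with a sample size of 20". For the untreated, unfit cohort, "The sample size is 30 for Cohort C3, which will provide adequate precision of efficacy estimates", with exact 90% intervals in Table 8-2. SAP 1.3 repeats these figures, except that its 30 are made up of 27 Cohort C3 subjects plus Phase 1b subjects ("including 3 subjects in Group C Phase 1b who were previously untreated AML, unfit for Group A or B").

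The reporting text works at the 95% level. Protocol 8.3.1 sets the default: "Unless otherwise indicated, 95% CIs for binary variables will be calculated using the binomial distribution (exact method) and will be 2 sided". Protocol 8.5.1, on response rates, says: "For all analyses, the corresponding 95% exact CIs will be presented". SAP 6.1.2 agrees: "the corresponding 95% exact CIs based on Clopper-Pearson method will be presented". No section plans a 90% interval for a response rate. Protocol 8.6.2 does plan 90% intervals for the DLT rate, so both levels have a place in the trial.

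**The concern.** For these three cohorts, interval width is the main statistical argument for the chosen size. If the promised precision is at one level and the reported interval at another, a reader who compares the study report with the protocol will find wider intervals than the sizing text led them to expect, with no explanation in either document. Group A's stated distance of about 7-14 points would not be met by the reported intervals at n=40.

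The sizing text also sets historical rates beside these intervals: 52% for 7+3, and 20-30% for standard treatment in the Group B setting. A narrower planning interval makes the separation from those rates look better than the reported interval would. At stake would be an overstatement of how informative each cohort can be.

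**Working it through.** **Inputs.** Sizes and assumed rates come from Protocol 8.9 and SAP 1.3: n=40 at 70%, 80% and 90%; n=20 at 50%; n=30 at 30%, 50% and 70%. The method is the two-sided exact (Clopper-Pearson) interval named in SAP 6.1.2.

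**Formula.** For x responders out of n at level 1-α, the lower limit is the α/2 quantile of Beta(x, n-x+1), and the upper limit is the 1-α/2 quantile of Beta(x+1, n-x). Take α=0.10 to reproduce the plan and α=0.05 for the reporting level.

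**Results (limits in %, width ratio from unrounded limits).**

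| x/n | Plan, 90% | Recomputed 90% | Exact 95% | Width ratio 95/90 | Largest shift of a limit (points) |
|---|---|---|---|---|---|
| 28/40 | 56-82 | 55.97-81.69 | 53.47-83.44 | 1.165 | 2.50 |
| 32/40 | 67-90 | 66.80-89.64 | 64.35-90.95 | 1.164 | 2.45 |
| 36/40 | 79-97 | 78.56-96.51 | 76.34-97.21 | 1.163 | 2.22 |
| 10/20 | 30-70 | 30.20-69.80 | 27.20-72.80 | 1.151 | 3.00 |
| 9/30 | 17-47 | 16.63-46.51 | 14.73-49.40 | 1.160 | 2.89 |
| 15/30 | 34-66 | 33.89-66.11 | 31.30-68.70 | 1.161 | 2.59 |
| 21/30 | 53-83 | 53.49-83.37 | 50.60-85.27 | 1.160 | 2.89 |

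All seven planning intervals reproduce to the rounding shown.

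**Group A distance statement.** At 90% the smallest distance is 96.51 - 90 = 6.5 points and the largest is 70 - 55.97 = 14.0, which matches the stated 7-14. At 95% these become 97.21 - 90 = 7.2 and 70 - 53.47 = 16.5, so about 7-17.

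**Against the quoted historical rates.** In Group A at 70%, the lower limit exceeds 52% at either level: by 55.97 - 52 = 4.0 points at 90%, and by 53.47 - 52 = 1.5 points at 95%. In Group B at 50%, the lower limit goes from 30.2%, just above the 20-30% range, to 27.2%, inside it.

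**What uses these limits.** SAP section 3 makes the analysis descriptive. Protocol 8.9 leaves the comparison of the Group B arms to the clinical data as a whole. The one numerical efficacy rule, Cohort C1A futility, counts responders (5 of 15) and uses no interval. Cohort C2's size rests on practical considerations, with no interval quoted.

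**The case for a change.** The best case for a change is that precision was promised at one level and will be delivered at another without disclosure, and that the Group B lower limit crosses into the historical range when the level changes. Pooling phases does not dispose of this, because SAP Table 3-2 keeps a separate column for Group A Phase 2, where the n=40 interval applies directly.

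Those facts stand. They do not make a defect. Each interval is labelled with its level wherever it appears, so a reader can see that the levels differ, and neither document claims that the 7-14 point distance holds at 95%. Using one level to illustrate planning precision and another to report is permissible. The Group B crossing would matter only if the plan required the interval to exclude 30%, and it does not.

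A further argument is that achieved precision is worse still. Protocol 3.1.6 says: "This amendment identifies the closure of Cohort C3 to further enrollment (n=12". SAP section 1 says that Group B Phase 2 closed before reaching its target. That is a matter of achieved size, not of 90% against 95%, and both closures are already disclosed. Adding a precision figure for n=12 would also need a chosen rate. At 50% the exact 95% interval is 21-79%, but SAP section 1 reports a lack of responses to monotherapy, and 0 of 12 would give 0-26%. The SAP also pools eligible Phase 1b subjects with Cohort C3 for this analysis, so n=12 is not the only relevant denominator.

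**Conclusion.** No change is needed. The sizing intervals are correct at the level they state, and the reporting level is stated clearly and consistently in both documents. At the planned sizes, moving from 90% to 95% widens the intervals by 15-17% and shifts no limit by more than 3.0 points. That would not lead anyone to a different cohort size, since no rule ties size or success to a limit.

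With enrolment completed or terminated in every cohort, adding 95% figures to the sizing section could not affect design or analysis. Following the plan as written gives valid exact 95% intervals at the achieved sizes, which is what a reader of the results needs. At most, one sentence in SAP 1.3 could say that planning used 90% and reporting uses 95%; that is an editorial courtesy.

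This conclusion assumes the planned sizes and assumed rates in Protocol 8.9 and SAP 1.3, and that the analysis stays descriptive.

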Cohort C1A: This cohort is designed to enroll 6 R/R AML subjects first. Nine Group C Phase 1b subjects who were R/R AML and received at least 21 days of ENTO (400 mg or 800 mg) and Cohort C1A subjects will be pooled to provide an adequate sample size (n=15) for the following futility analysis for subjects with R/R AML. If 5 or more of the initial 15 subjects achieve CR/CRi after 1-2 cycles, an additional 15 subjects will be enrolled. However, if less than 5 of the initial 15 subjects achieve CR/CRi after 1-2 cycles, then treatment would be considered futile. At the time of amendment 7, futility has been met and, thus, Cohort C1A will not move forward (ie, will not enroll any subjects).

Cohort C2: This cohort is designed to enroll 15 subjects with R/R AML subjects with MLL gene rearrangement.

Cohort C3: This cohort is designed to enroll 27 previously untreated AML subjects who are unfit (eg, very elderly, have multiple comorbidities, and a poor Eastern Cooperative Oncology Group (ECOG) performance status) for chemotherapy or hypomethylating agent, or refuse either of these 2 treatment options. Three Group C Phase 1b subjects who were previously untreated AML, unfit for Group A or B, and received at least 21 days of ENTO (400 mg or 800 mg), and Cohort C3 subjects will be pooled to provide an adequate sample size (n=30) for the efficacy analysis for subjects with previously untreated AML and unfit for Group A or B. Amendment 7 identifies early enrollment closure of this cohort.

The study procedures for all treatment groups/cohorts are presented in Appendix 2 of the study protocol.

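### The previously untreated, unfit cohort (C3) is still described as 30 subjects with adequate precision, although the same amendment closed it at 12; the tabulated precision will not be achieved

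*Protocol*

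**What the plan says.** **Planned size.** Protocol 8.9 says "The sample size is 30 for Cohort C3, which will provide adequate precision of efficacy estimates". It then refers to Table 8-2, which "provides the 90% confidence interval (CI) of 30 subjects for the assumed composite complete remission rate". Protocol 3.1.6 also lists C3 as 30 subjects. SAP 1.3 builds the same total differently: "The sample size is 30 for previously untreated AML (unfit for Group A or B"). Three of the 30 come from Phase 1b; the rest are given as "27 subjects in Cohort C3, which will provide adequate precision of efficacy estimates". SAP Table 1-3 repeats the Table 8-2 intervals. SAP 1.2 and 3.2 justify the pooling of Phase 1b with C3 on the ground that it gives a large enough sample for the efficacy analysis.

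**Closure.** Protocol 3.1.6 opens with a note: "This amendment identifies the closure of Cohort C3 to further enrollment (n=12"). The synopsis carries the same note, with the same count, in its study design text and at the end of its sample size text. SAP 1.2 says "Amendment 7 identifies early enrollment closure of this cohort". I found no achieved C3 number in the SAP.

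**Reporting.** SAP 6.1.2 will report Group C remission rates with exact 95% Clopper-Pearson intervals. The planning tables use 90%.

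**The concern.** Section 3.1.6 of the protocol carries both 12 and 30 for the same cohort. Section 8.9 was partly brought up to date: it records that Cohort C1A met futility and will not continue. It has no matching line for C3, and its Group C total of 74 still counts 60 in Phase 2. The SAP was written after recruitment had stopped, yet SAP 1.3 still describes the size and its precision in the present and future tense.

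Composite complete remission is a primary efficacy endpoint, and the pooled untreated population is a planned efficacy analysis that the SAP justifies by its sample size. If the study report draws its sample size section from SAP 1.3, it will attach to this population a size and a precision that it does not have.

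**Working it through.** **Inputs**
- Planned n = 30: Protocol 8.9; SAP 1.3 as 27 + 3.
- C3 at closure: 12 (Protocol synopsis and 3.1.6).
- Phase 1b subjects to be pooled: 3 (SAP 1.3).
- Assumed rates 30%, 50%, 70% and exact two-sided 90% intervals (Table 8-2).
- Reporting level 95%, Clopper-Pearson (SAP 6.1.2).

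**Formula.** For x responders among n, with α = 0.10 or 0.05:
- lower limit = the α/2 quantile of Beta(x, n−x+1)
- upper limit = the 1−α/2 quantile of Beta(x+1, n−x)
- for x = 0, the upper limit is 1 − (α/2)^(1/n)

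**Step 1: reproduce the plan's figures (n=30, 90%).** 9/30 gives 16.6–46.5%, 15/30 gives 33.9–66.1%, and 21/30 gives 53.5–83.4%. Both tables are right for 30 subjects.

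**Step 2: which n applies.** If the 12 counts C3 alone, the pooled n is 12 + 3 = 15. The protocol, however, gives C1A as 15, where the SAP has 6 in C1A plus 9 from Phase 1b (6 + 9 = 15). The protocol's planned 30 for C3 likewise equals the SAP's 27 + 3. Under that counting convention the 12 may already contain the 3, which leaves 9 in C3 proper and 12 pooled. Both sizes are therefore carried forward.

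**Step 3: the same assumed rates at those sizes.** The formula is evaluated at x = n × rate, which is fractional in places, so that only n changes.

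| Rate | 90%, n=30 (stated) | 90%, n=15 | 90%, n=12 | 95%, n=15 | 95%, n=12 |
|---|---|---|---|---|---|
| 30% | 17–47% | 11.9–54.5% | 10.2–57.7% | 9.7–58.4% | 8.0–62.0% |
| 50% | 34–66% | 27.1–72.9% | 24.5–75.5% | 23.9–76.1% | 21.1–78.9% |
| 70% | 53–83% | 45.5–88.1% | 42.3–89.8% | 41.6–90.3% | 38.0–92.0% |

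Counts that can actually occur agree. At 90%, 4/12 gives 12.3–60.9%, 8/12 gives 39.1–87.7%, 5/15 gives 14.2–57.7%, and 10/15 gives 42.3–85.8%.

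**Step 4: width.** At 50% and the 90% level:
- n=30: 66.1 − 33.9 = 32.2 points
- n=15: 72.9 − 27.1 = 45.8 points, ratio 45.8/32.2 = 1.42
- n=12: 75.5 − 24.5 = 51.0 points, ratio 51.0/32.2 = 1.58

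**Step 5: no responders.** SAP section 1 cites lack of response to monotherapy among the reasons for stopping recruitment, so low counts are worth showing. The 95% upper limits are:
- n=12: 1 − 0.025^(1/12) = 26.5%
- n=15: 1 − 0.025^(1/15) = 21.8%
- n=30: 1 − 0.025^(1/30) = 11.6%

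**The case against.** The best defence is that a sample size section records the design, and a design is not rewritten because enrolment stopped early. SAP 1.3 also keeps about 40 randomized subjects for Group B, although SAP section 1 says that recruitment closed short of plan. The closure of C3 is disclosed, including directly after the synopsis points to Section 8.9. The study report will show the observed numbers and exact 95% intervals computed from them, and no test or decision rule for C3 depends on 30.

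Much of this stands, and it rules out several stronger readings that a reader might infer:
- **That Tables 8-2 and 1-3 are miscalculated.** They reproduce.
- **That the closure was concealed.** It is stated repeatedly.
- **That the pooled size is known to be 15.** Neither document prints 15 for this population, and the C1A counts point to another possibility.
- **That the plan promised to separate particular remission rates.** Table 8-2 makes no such claim. Its own intervals overlap between 30% and 50%, and between 50% and 70%.
- **That 30 should be overwritten.** That would make 12 or 15 look like the intended size.

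What the defence does not answer is that the text is not marked as historical. Section 8.9 was updated for C1A and not for C3, and 3.1.6 gives both numbers without reconciling them. SAP 3.3 puts the Group B randomization target in the past tense as a plan; SAP 1.3 does not do so for this cohort.

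**Conclusion.** The point holds as an internal inconsistency. Protocol 8.9 and 3.1.6 and SAP 1.3 and 3.2 describe a size, or an adequacy, that the same amendment had already ruled out. At equal assumed rates the intervals are about 1.6 times the stated width with 12 subjects and about 1.4 times with 15. Neither size reaches the tabulated precision, so the conclusion does not depend on which one is right.

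It rests on three assumptions. No one joined C3 after the closure. All 12 received at least one dose and so enter the Full Analysis Set; if fewer did, the intervals widen further. The shortfall is measured against Table 8-2, because neither document gives a numerical criterion for adequate precision. The planned analysis method is unaffected, and the observed intervals will be valid at whatever n is achieved.

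**What to change.** 1. In SAP 1.3, and in Protocol 8.9 and 3.1.6 if the protocol is amended again (otherwise in the study report), label 30 as the originally planned size and keep Tables 8-2 and 1-3 under that label.
2. State the achieved number. Say whether the 12 already includes the 3 Phase 1b subjects, so that the pooled n is fixed at 12 or 15.
3. Add exact intervals at the achieved n, at the 95% level of SAP 6.1.2, including the case of no responders.
4. Remove or qualify the precision claim in Protocol 8.9 and SAP 1.3, and the matching sample size claim in SAP 1.2 and 3.2.

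The cost is a few sentences and one small table, with no change to conduct or analysis. The stated precision becomes less favourable.
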